Winship Protocol #: 4457-18; Version 6.0 04 05 2021

TITLE: A Randomized Phase 2 Study of Rituxan Hycela in patients with advanced melanoma undergoing combination immune checkpoint blockade with nivolumab and ipilimumab.

*Principal Investigator: [name].

[name]

[name] [contact] (phone) [contact] (fax)

[contact]

Co-Investigators: [name].

[name] [contact](phone) [contact] (fax) [contact]

[name].

[name], M.D.

[name]. [name]. [name]

Statistician:

[name] Ph.D Winship Cancer Institute of Emory University [name] Tel (O): [contact] [contact]

[figure not shown]
Study Coordinator:

[name] [name] [contact] (phone) [contact] (fax) [contact]

Supplied Agent: Rituximab (supplied by Genentech, South San Francisco, CA)

IND: Exempt

SCHEMA

Trial Design. All patients have chosen ipi/nivo as standard of care (SOC) treatment. They will be randomized prior to the first dose of ipi/nivo to receive either ARM A: SOC Ipilimumab + Nivolumab only with no additional therapy or ARM B: Standard of care Ipilimumab and Nivolumab, + 4 weekly doses of Rituxan (first dose of IV Rituxan followed by 3 weekly doses of subcutaneous Rituximab hycela) beginning 1-2 days following the first dose of Ipilimumab and Nivolumab. SOC Ipi/Nivo is ipilimumab 3mg/kg every 3 weeks for 4 doses and nivolumab 1mg/kg every 3 weeks for 4 doses followed by nivolumab 480 mg IV every 4 weeks x 12 doses or until disease progression or intolerant adverse event.

This is a prospective randomized trial to test the efficacy of preemptive Rituxan in melanoma patients in reducing Immune-related adverse events (IRAEs) following combination checkpoint blockade (CCB). All eligible patients will undergo baseline evaluation to assess the status of disease as well as a baseline tumor biopsy. Combination checkpoint blockade will be administered as per current FDA approved standard of care, consisting of nivolumab at a dose of 1 mg/kg and ipilimumab at a dose of 3 mg/kg every 3 weeks for 4 doses, followed by nivolumab maintenance at a dose of 480 mg every 4 weeks x 1 year. Patients will be randomly assigned to no additional therapy (ARM A control) or 4 weekly doses of Rituxan for B cell depletion (ARM B). Rituxan will be administered as 375 mg/m2 IV for the first dose followed by weekly subcutaneous dosing at 1400 mg dose of Rituxan Hycela for weeks 2-4, as per recommended dosing for the FDA approval in the setting of lymphoma. All patients will be clinically monitored for the development of IRAEs utilizing NCI Common Toxicity Criteria v5.0. Any patient who received at least one dose of study drug will be included in safety analysis, and safety assessment will continue through treatment phase and up to 100 days after the last dose of study drug. Tumor response will be assessed according to the Response Evaluation Criteria in Solid Tumors (RECIST v1.1) and irRECIST at 12 weeks and every 12 weeks thereafter. All patients will also undergo pre treatment and post treatment biopsies if possible.

TABLE OF CONTENTS

SCH	EMA	3								
1.	OBJECTIVES	6								

1. OBJECTIVES

1.1 Primary Objectives

• To compare rates for Grade 3-4 IRAEs in the first 6 months in patients treated with combination checkpoint blockade (CCB) therapy (anti-CTLA4 and anti-PD1) as a part of standard of care for advanced melanoma who are treated with a single course of 4 weekly doses of Rituxan therapy versus those who are not treated with Rituxan.

1.2 Secondary Objectives

- To evaluate the safety and tolerability (in terms of Rituxan-related adverse events) in patients with melanoma receiving CCB.
- To compare objective response rate in patients receiving CCB therapy + Rituxan versus CCB therapy alone.
- To compare 1 year overall and progression-free survival in patients receiving CCB therapy + Rituxan versus CCB therapy alone.
- To compare changes in CD21^{lo} B cells in patients receiving CCB therapy + Rituxan versus CCB therapy alone.
- To compare changes in T cells in patients receiving CCB therapy + Rituxan versus CCB therapy alone.

Exploratory Objectives

• To compare treatment induced changes in tumor tissue in patients receiving CCB therapy + Rituxan versus CCB therapy alone.

2. BACKGROUND

2.1 Study Disease(s)

Stage IIII or IV unresectable melanoma

2.2 IND Agent(s)

Rituxan Hycela

Rituxan Hycela is a combination of rituximab, a CD20-directed cytolytic antibody, and hyaluronidase human, an endoglycosidase, indicated for the treatment of adult patients with Follicular Lymphoma (FL), Diffuse Large B-cell Lymphoma (DLBCL), and Chronic Lymphocytic Leukemia (CLL). Rituxan has also been extensively utilized for therapy of autoimmune disorders such as immune thrombocytopenic purpura. The proposed use of Rituxan in this study is based on new data from the PI regarding the role of CD21^{lo}CD20⁺ B cells in the pathogenesis of immune related adverse events following combination checkpoint blockade.

Please note Rituxan Hycela is always given as Rituximab IV as the first dose, if no reaction can proceed to Rituxan Hycela.

2.3 Rationale

Immune related adverse events (IRAEs) as a limiting toxicity of combination checkpoint blockade:

Blockade of T cell immune checkpoints PD-1/PD-L1 and CTLA-4 has emerged as an effective therapy for melanoma(1-4). Immune checkpoint blockade with monotherapy (anti-CTLA4 or anti-PD-1 alone) leads to tumor regression in only a subset of patients and combination therapy has therefore, been explored as a strategy to enhance clinical efficacy. The best studied combination therapy (concurrent administration of PD-1 and CTLA-4 blockade) leads to high response rates in advanced melanoma(5-10). However, increase in tumor regressions following combination therapy is associated with a marked increase in Grade 3 and 4 IRAEs resulting in significant morbidity and discontinuation of therapy in up to one third of patients(11, 12). Reduction in antibody dosages may be one way to partly reduce the risk for IRAEs with combination therapy, however the impact of such strategy on clinical efficacy remains to be resolved(13). There remains an urgent need to better understand the pathogenesis of IRAEs following CCB therapy and how/whether they can be prevented. Ability to prevent these IRAEs will have a major impact on the applicability of combination immune checkpoint blockade as therapy in melanoma as well as other cancers. This is not just because of short-and long-term morbidity and costs associated with IRAEs, but also because IRAEs often prevent delivery of planned therapy in several patients.

Importance of human studies to test biomarkers and prevention of IRAEs following checkpoint blockade:

As discussed above, clinical studies have shown that immune checkpoint blockade therapies can lead to distinct patterns of autoimmunity in the clinic. Importantly, the pattern or spectrum of autoimmune manifestations observed in the clinic were not entirely predictable from preclinical studies of immune checkpoint blockade(14-16). Whether these differences related to species-specific (human versus mouse) differences in the biology of the target organ(s), or the immune system remain to be clarified. A relevant example are the findings about changes in B cells in humans with CTLA4 deficiency, which were not anticipated from prior studies in CTLA4-deficient mice. In addition, the biology of the specific immune cell types may also potentially differ between mouse and man. However, these considerations do raise the importance of directly studying patients to gain fundamental insights into effects of immune checkpoint blockade. Mechanistic studies in humans are limited, but controlled studies that link targeted manipulation of specific cell types or pathways provide an opportunity to gain fundamental mechanistic insights with immediate translational potential.

Changes in B cells and risk of IRAEs following combination checkpoint blockade:

Our studies are among the first to identify that early changes in circulating B cells correlate with the development of IRAEs following checkpoint blockade(17). Much of the attention in terms of understanding biomarkers of response or efficacy in this setting has to date been focused on T cell responses. Changes in B cells have received less attention(18). In our preliminary studies, changes in B cells not only correlated with the development and severity of IRAEs, these

changes preceded the clinical manifestations of IRAEs by several weeks. Our studies will therefore provide a novel biomarker to help identify patients at risk for the development of IRAEs following checkpoint blockade. Importantly, these studies involve flow-based assays on circulating immune cells, and therefore can be easily incorporated into routine clinical practice.

B cell depletion as a preemptive strategy to lower IRAEs:

The discovery that patients who experience early changes in B cells following CCB therapy are at higher risk for subsequent development of IRAEs provides the opportunity to prevent IRAEs in this cohort. These studies will test a novel strategy of B cell depletion to reduce the risk of autoimmunity following combination checkpoint blockade. This is feasible because CCB-emergent changes in B cells not only precede autoimmune complications but are also directly amenable to targeting via anti-CD20 antibodies. It is important to note that even if this approach does not work clinically, it will provide biologically and clinically important information. For example, it would then suggest a role of other immune cells in mediating IRAEs. Recent studies have suggested that B cell depletion may also enhance anti-tumor effects in melanoma and therefore this combination may not only reduce toxicity but also improve efficacy(19).

2.4 Correlative Studies Background

CD21^{lo} B cells as targets in IRAEs following combination checkpoint blockade:

Our studies are also among the first to identify a role for CD21^{lo} subset of B cells in CCB-induced IRAEs. Our preliminary data indeed identified this as a specific subset of human B cells that express PD1. Improved understanding of the biology of this specific B cell subset in melanoma patients and changes in these cells following CCB will therefore provide novel mechanistic insights into CCB-induced IRAEs. These studies may also suggest novel approaches to specifically target this specific subset, as opposed to the current strategy targeting all B cells to lower the risk of IRAEs.

Contributions of B cells to protective immunity mediated by combination checkpoint blockade:

While the role of T cells in protective immunity is well established, the relative contribution of B cells to the anti-tumor effects of checkpoint blockade remain to be clarified, particularly in human studies. In preclinical models, depletion of B cells did not lead to reduction in anti-tumor effects of checkpoint blockade(19). The application of B cell depleting antibody with Rituxan in patients undergoing CCB will provide direct and novel insights into the role of B cells in both IRAEs and tumor immunity. The latter is particularly relevant because approaches targeting IRAEs will only be clinically viable if they do not adversely impact protective tumor immunity or alter the frequency or durability of clinical tumor regressions following CCB therapy.

3. PATIENT SELECTION

3.1 Eligibility Criteria

Inclusion Criteria

Subjects must meet all of the inclusion criteria before enrollment can occur.

• Clinically eligible to receive FDA approved standard of care combination immune

Version Date: 04-05-2021 v6.0

checkpoint therapy with Ipilimumab and Nivolumab for unresectable Stage III or stage IV melanoma.

- Age \geq 18 years.
- Patients with progression on anti-PD-1 as a single agent are allowed to enroll on the study
- No therapy with immune checkpoint inhibitors other than anti-PD-1 within 1 year prior to starting combination checkpoint therapy. Prior adjuvant ipilimumab as single agent is allowed if greater than 1 year since last treatment. Patient had no Grade 3 or 4 toxicities from the checkpoint inhibitors including prior single agent PD-1 or anti-CTLA4 therapy. History of adjuvant interferon is allowed.
- Patients must have the following required values for laboratory tests obtained within three weeks prior to randomization (ULN: institutional upper limit of normal):
 - o -Adequate blood counts: White Blood Count \geq 3,000/uL ANC \geq 1,500/uL, Platelet Count \geq 100,000/uL, Hemoglobin \geq 9 g/dL,
 - o -Adequate renal function: Serum creatinine ≤1.5 x ULN or serum creatinine clearance (CrCl) ≥ 40ml/min. (CrCl= Wt (kg) x (140- age)*/72 x Cr. level, *female x 0.85)
 - o -Adequate liver function: AST and ALT ≤3 x ULN (≤5 x ULN for patients with documented liver metastases), Alkaline phosphatase ≤ 2X ULN (≤5XULN for those with bone metastasis), Total bilirubin ≤ 1.5 X ULN except those with direct bilirubin or gilberts syndrome, serum LDH ≤10_X ULN).

Exclusion Criteria

Subjects will be ineligible for enrollment if they meet any of the following criteria.

- Allergy to Rituximab, or any of the ingredients in Rituximab injection or Rituximab and hyaluronidase human injection.
- Patients with active CNS metastatic disease or leptomeningeal disease. Patients with CNS metastatic disease that has been treated with surgical resection or stereotactic radiosurgery are eligible if lesions are stable. If patient required steroid therapy for his CNS metastatic disease, the patient maybe enrolled 2 weeks after stopping steroids. Prior therapy with immune checkpoint blocking antibodies (monotherapy given at least 1 year prior to starting combination therapy and no Grade 3-4 toxicities while on monotherapy are allowed, prior vaccines or IL2 given at least one year prior is also allowed)
- Patients may have had prior systemic therapy in the adjuvant setting (e.g. interferon, BRAF, or MEK agents). Adjuvant ipilimumab as single agent is allowed if greater than 1 year since last treatment and patient had no Grade 3 or 4 toxicities from the checkpoint inhibitors. Prior anti-PD-1 therapy is allowed if patients progress and have had no grade 3 or 4 toxicities related to anti-PD-1 therapy.
- Women must not be pregnant or lactating. Must have negative urine or blood pregnancy test within 1 week of starting therapy.
- Patients with known HIV are ineligible
- Patients with active Hepatitis B Virus (HBV) or Hepatitis C virus (HCV) are ineligible. Patients with prior history of, or serology suggestive of prior infection with

Version Date: 04-05-2021 v6.0

Hepatitis B Virus (HBV) or Hepatitis C virus (HCV) are also ineligible.

- Patients with active, known or suspected autoimmune disorders including lupus and type I diabetes are ineligible. Patients with history of vitiligo, thyroiditis are eligible.
- Patients with active or history of inflammatory bowel disease are ineligible.
- Patients cannot be on corticosteroid therapy except as physiologic replacement therapy.
- Patients receiving ongoing corticosteroid therapy for autoimmune disorders are ineligible. Occasional steroid inhaler use or nasal spray are allowed. Patients receiving replacement doses of steroids for adrenal insufficiency are eligible.
- Patients must not have any serious underlying medical conditions or take medications
 that in the investigators opinion may interfere with compliance or interpretation of
 IRAEs.

3.2 Inclusion of Women and Minorities

Both men and women of all races and ethnic groups are eligible for this trial. Due to melanoma being at a much higher incidence in Caucasians as compared to other races, we expect the vast majority of subjects to be Caucasian.

4. REGISTRATION PROCEDURES

4.1 Central Registration Process

This occurs at the time a subject is consented.

4.1 a Local Winship Procedures

To register a patient, the following documents should be completed by the Study Coordinator and e-mailed to Clinical Research (OCR) [contact] and Winship Central Subject Registration (WCSR) [contact] within 24 hours or 1 business day:

- Signed patient consent form
- HIPAA authorization form
- Emory Research Management System (ERMS) Enrollment Fax Cover
 - o printed from ERMS (https://erms.emory.edu) after subject registered

Enrolling a subject requires careful screening and determination of eligibility.

Eligible patients will be enrolled on study centrally at Winship Cancer Institute by the Study Coordinator.

Agents may be ordered by a participating site only after the initial IRB approval.

4.2a Local Site

When all required test results are available, complete the eligibility checklist and provide the checklist and the supporting documentation to the IRB approved investigator for review and sign-off. Once the investigator has signed the eligibility checklist, randomization and or enrollment may proceed. Oncore and ERMS must be updated to

Version Date: 04-05-2021 v6.0

reflect eligibility and on treatment status.

5. TREATMENT PLAN

5.1 Agent Administration

Once the investigator has signed the eligibility checklist, randomization may proceed. Patients meeting study entry criteria will be randomized to treatment ARM A or Arm B by the study statistician, [name]. Eligible subjects (eligibility confirmed and checklist signed) will be assigned to a treatment arm until 44 subjects (22 in each arm) have been enrolled. The study coordinator will update Oncore and ERMS reflect randomization information.

Following randomization, patients should begin protocol treatment within 5 business days. Issues that would cause treatment delays should be discussed with the Principal Investigator.

Treatment will be administered on an *outpatient* basis. Reported adverse events and potential risks are described in Section 7. Appropriate dose modifications are described in Section 6. No investigational or commercial agents or therapies other than those described below may be administered with the intent to treat the patient's malignancy.

Patients will be randomly assigned 1:1 using block randomization with a block of 6 patients. Randomization schema will be kept in the research pharmacy.

Patients with unresectable stage III or stage IV melanoma being treated with FDA approved standard of care immune checkpoint combination therapy with Ipilimumab and Nivolumab are eligible for this trial.

Patients will be randomized 1:1 to either continue therapy with standard of care Ipilimumab and Nivolumab (ARM A) or standard of care Ipilimumab and Nivolumab plus **4 doses of weekly Rituxan** (ARM B).

Patients enrolling on this study following treatment failure on single agent anti-PD-1 will be distributed equally between arms A and B of the study.

Induction Phase:

ARM A: Cycles 1-4

Each cycle is 21 days and includes Ipilimumab (3 mg/kg) on day 1 plus Nivolumab (1 mg/kg) on Day 1.

ARM B. Cycles 1-4

Each cycle is 21 days and includes Ipilimumab (3 mg/kg) on day 1 plus Nivolumab (1 mg/kg) on

Version Date: 04-05-2021 v6.0

Day 1. In addition, patients will receive 4 weekly doses of Rituxan (first dose 375 mg/m2 IV and then 3 weekly doses of 1400 mg Rituxan Hycela subcutaneous, as per current label for Rituxan Hycela).

First dose of Rituxan will be administered 1 week after start of Ipi/Nivolumab therapy. 3rd dose of Rituxan will be administered on day 2 of cycle 2 after infusion of Ipi/Nivo on week4.

Continuation Phase:

All patients will receive Nivolumab 480 mg every 4weeks for up to 13 doses (52 weeks) until disease progression or intolerable adverse events.

All treatments will have a \pm -3 business day window for administration.

5.1.1 *IND Agent(s)*

Rituximab (RITUXAN) (for IV use)

Dosage and administration:

Do not administer as an intravenous push or bolus. RITUXAN should only be administered by a healthcare professional with appropriate medical support to manage severe infusion-related reactions that can be fatal if they occur. Pre-medicate before each infusion.

Prior to First Infusion: Screen all patients for HBV infection by measuring HBsAg and anti-HBc before initiating treatment with RITUXAN. Obtain complete blood counts including platelets (CBC) prior to the first dose.

During RITUXAN Therapy: In patients with lymphoid malignancies, during treatment with RITUXAN monotherapy, obtain complete blood counts (CBC) with differential and platelet counts prior to each RITUXAN course. During treatment with RITUXAN and chemotherapy, obtain CBC with differential and platelet counts at weekly to monthly intervals and more frequently in patients who develop cytopenias. In patients with RA, GPA or MPA, obtain CBC with differential and platelet counts at two to four month intervals during RITUXAN therapy. Continue to monitor for cytopenias after final dose and until resolution.

First Infusion: Initiate infusion at a rate of 50 mg/hr. In the absence of infusion toxicity, increase infusion rate by 50 mg/hr increments every 30 minutes, to a maximum of 400 mg/hr.

Storage and Handling:

RITUXAN vials [100 mg/10 mL single-use vials (NDC 50242-051-21) and 500 mg/50 mL single-use vials (NDC 50242-053-06)] are stable at 2°C–8°C (36°F–46°F). RITUXAN vials should be protected from direct sunlight. Do not freeze or shake.

Rituxan Hycela:

RITUXAN HYCELA is for subcutaneous use only. RITUXAN HYCELA should only be administered by a healthcare professional with appropriate medical support to manage severe reactions that can be fatal if they occur. All patients must first receive at least one full dose of a rituximab product by intravenous infusion without experiencing severe adverse reactions before

starting treatment with RITUXAN HYCELA. If patients are not able to receive one full dose by intravenous infusion, they should continue subsequent cycles with a rituximab product by intravenous infusion and not switch to RITUXAN HYCELA until a full intravenous dose is successfully administered. Refer to the prescribing information for a rituximab product for intravenous infusion for additional information (Rituxan prescribing information, Genentech).

Premedicate approximately 30 minutes before each dose of RITUXAN HYCELA. Dose reductions of RITUXAN HYCELA are not recommended. The recommended dose is RITUXAN HYCELA 1,400 mg/23,400 Units (1,400 mg rituximab and 23,400 Units hyaluronidase human) subcutaneously at a fixed dose irrespective of patient's body surface area. The dosing for Rituxan Hycela utilized in this protocol is similar to that FDA approved for follicular lymphoma.

Recommended Premedication and Prophylactic Medications: Premedicate with acetaminophen and an antihistamine before each dose of RITUXAN HYCELA.

Administration and Storage

RITUXAN HYCELA is ready to use. To avoid needle clogging, attach the hypodermic injection needle to the syringe immediately prior to administration. RITUXAN HYCELA is compatible with polypropylene and polycarbonate syringe material and stainless steel transfer and injection needles. Use the product immediately. Parenteral drug products should be inspected visually for particulate matter and discoloration prior to administration. RITUXAN HYCELA should be a clear to opalescent and colorless to yellowish liquid. Do not use vial if particulates or discoloration is present.

Administration

- Inject RITUXAN HYCELA into the subcutaneous tissue of the abdomen over approximately 5–7 minutes and never inject into areas where the skin is red, bruised, tender or hard, or areas where there are moles or scars. No data are available on performing the injection at other sites of the body.
- Inject 11.7 mL of RITUXAN HYCELA 1,400 mg/23,400 Units vial (1,400 mg rituximab and 23,400 Units hyaluronidase human) subcutaneously into the abdomen over approximately 5 minutes.

If administration of RITUXAN HYCELA is interrupted, continue administering at the same site, or at a different site, but restricted to the abdomen.

During treatment with RITUXAN HYCELA, do not administer other medications for subcutaneous use at the same sites as RITUXAN HYCELA.

Storage:

After the solution of RITUXAN HYCELA is withdrawn from the vial, it should be labeled with the peel-off sticker and used immediately. If not used immediately, prepare in controlled and validated aseptic conditions. Once transferred from the vial into the syringe, store the solution of RITUXAN HYCELA in the refrigerator at 2°C-8°C (36°F-46°F) up to 48 hours and

subsequently for 8 hours at room temperature up to 30°C (86°F) in diffuse light.

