14.2 Sample Size/Accrual Rate

This is an open-label, 2-arm phase II clinical trial to study the differential effect in the risk of IRAEs between treatment and control groups. A sample size of 22 patients per arm (44 total) will provide us approximately 80% power to detect a 40% difference in the rates of developing ≥grade 3 IRAE within 6 months follow up between the control and the treatment arm (estimated to be 60% in the control arm, Callahan et al; J Clin Oncol. 2017 Dec 1;35(34):3815-3822). The sample size calculation is based on Fisher's exact test at a one sided significance level of 0.05 under the following assumptions: 1). Patients will be randomized in 1:1 ratio of the treatment to control arm. 2). Approximately 60% patients in the placebo arm will develop > grade 3 IRAE

within 6 months based on our pilot study. 3). The treatment will reduce the rate of ≥ grade 3 IRAE to 20% in the treatment arm. In a recent study, the rate of objective response following combination checkpoint blockade was 42% (Callahan et al; J Clin Oncol. 2017 Dec 1;35(34):3815-3822). In order to monitor potentially adverse impact of Rituxan on checkpoint blockade, we will utilize early stopping rules based on an adaptive design wherein trial will be stopped if we have strong evidence of rates of objective response of <30%. The trial will be stopped early in the unlikely event that less than 2 patients among the first 12 patients treated by Rituxan respond to therapy. If the rate of objective response is > 30%, the probability that at least two out of first twelve patients will achieve an objective response of at least a PR for the first 12 patients is approximately 92%. Hazard ratios and corresponding two-sided 95% confidence intervals will be estimated using Cox-proportional hazards model, with the treatment group as a single covariate. Progression-free and overall survival curves, median with 95% confidence intervals, and progression-free survival rates at 6 months will be estimated with the use of Kaplan-Meier method. Biostatistics support for the study will be provided by biostatistics core resource of Winship Cancer Center.

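### A single printed block size of 6 in an open-label trial weakens allocation concealment: about 9 to 11 of the 44 assignments can be known in advance

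*Combined protocol and SAP*

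**What the plan says.** Section 5.1 fixes the method: "Patients will be randomly assigned 1:1 using block randomization with a block of 6 patients". Section 14.2 adds: "This is an open-label, 2-arm phase II clinical trial". Accrual runs "until 44 subjects (22 in each arm) have been enrolled".

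The plan has concealment steps. In section 5.1, "Once the investigator has signed the eligibility checklist, randomization may proceed", and then "Patients meeting study entry criteria will be randomized to treatment ARM A or Arm B by the study statistician". The same section says "Randomization schema will be kept in the research pharmacy".

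On access to past assignments, section 4.1 says "Eligible patients will be enrolled on study centrally at Winship Cancer Institute by the Study Coordinator". Section 5.1 has the coordinator enter the randomization result in the two study systems.

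On strata, section 14.2 randomizes newly diagnosed patients and patients with earlier adjuvant anti-PD-1 treatment as separate groups. Section 5.1 speaks instead of spreading patients who failed single-agent anti-PD-1 equally over the arms. Neither place says whether blocks of 6 run within each group.

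Among the exclusions in section 3.1 are serious medical conditions or medications "that in the investigators opinion may interfere with compliance or interpretation of" IRAEs.

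**The concern.** With 3 places per arm in each block, the last places follow from the earlier ones. The block size stands in a document that study staff hold. Arm B visibly receives rituximab, and the person who enrols also keeps the record of assignments. Locking the list away stops staff from reading it. It does not stop them from deducing the next entry, and the deduction can be made before the eligibility checklist is signed.

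If someone who expects a given arm enrols, declines or delays a patient on that basis, the arms can differ at baseline in IRAE risk. With 22 patients per arm a few such decisions matter, and unrecorded selection cannot be fully undone in the analysis. The exclusion that turns on the investigator's opinion about interpreting IRAEs leaves some room for this.

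**Working it through.** **The plan's own figure.** The documents give no figure for predictability. The one related number is the power in section 14.2: 22 per arm, 60% against 20%, Fisher's exact test, one-sided 0.05, about 80%. Summing the binomial probabilities of all outcomes that the test rejects gives 79.1%, so it reproduces. It is used below only to cost the fix.

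**Inputs.** Block 6, ratio 1:1, so m = 3 places per arm (section 5.1); N = 44 (section 5.1); two separately randomized groups of unstated size (section 14.2). Assumption: the observer knows every earlier assignment in order and, if there are two lists, the patient's group.

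**Allocations known with certainty.** A block has C(6,3) = 20 equally likely orders. A place is determined once one arm is used up.

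| Position | Orders in which it is determined | Probability |
|---|---|---|
| 1 to 3 | 0 of 20 | 0 |
| 4 | 2 of 20 (first three alike) | 1/10 |
| 5 | 8 of 20 (first four split 3 to 1) | 2/5 |
| 6 | 20 of 20 | 1 |

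The sum is 1.5 per block, which agrees with 2m/(m+1) = 6/4. This is 25% of a full block.

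- One list: 44 = 7 × 6 + 2, so 7 × 1.5 + 0 = 10.5 (23.9%).
- Two lists, blocks of 6 in each: the lowest total comes when each list ends four places into a block (for example 4 and 40 patients, or 22 and 22): 6 × 1.5 + 2 × 0.1 = 9.2 (20.9%). The highest is 10.5.

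**Best guess.** Always guess the arm with more places left, and toss a coin at a tie. Expected correct guesses per block are m + (2^(2m)/C(2m,m) − 1)/2 = 3 + (64/20 − 1)/2 = 4.1, and 4.1/6 = 68.3%. For 44 patients on one list: (7 × 4.1 + 0.5 + 0.6)/44 = 67.7%. Chance alone gives 50%.

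**What varying blocks change.** Simulation for N = 44 on one list, with an observer who knows the set of sizes but not their order:

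| Block sizes | Known with certainty |
|---|---|
| 6 only | 23.9% (10.5 of 44) |
| 4 or 6 | 5.5% (about 2.4 of 44) |
| 4, 6 or 8 | 2.4% (about 1 of 44) |

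The best-guess rate hardly moves. The formula above gives 2.83, 4.10 and 5.33 correct guesses for blocks of 4, 6 and 8, and (2.83 + 4.10 + 5.33)/18 = 68.1%. Every block ends in balance, so guessing the arm that is behind does not require the block size.

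**What steering could do (illustration; its strength is assumed).** Suppose patients placed in known slots have IRAE risk d points higher in Arm A and d points lower in Arm B, with no true effect and 60% risk otherwise. The spurious difference is about 2 × 0.239 × d: 4.8 points for d = 10 and 9.6 points for d = 20. Simulated one-sided rejection rises from about 2.4% without steering to about 5% and 9%. At d = 10 this is still about the nominal 5%, because Fisher's test is conservative here.

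**The case against.** The strongest reply is that the plan does conceal allocation. The arm is assigned by the statistician, after sign-off, from a list kept in the pharmacy. This stands. A reader might infer from the open label and the printed block size that allocation is not concealed at all. The documents do not support that: 76% to 79% of assignments cannot be known with certainty.

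A second reply is that the documents place the running record with the coordinator and do not say that the investigators who judge eligibility see it. This also stands. Their access is plausible but undocumented, so the figures describe someone who tracks the sequence.

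Third, the room to steer is limited. The opinion-based exclusion covers serious conditions and medications, not patients in general. Autoimmune disease (apart from vitiligo or thyroiditis) and earlier grade 3 or 4 checkpoint toxicity are already excluded. The IRAE predictor that the protocol describes, early B-cell change, appears only after treatment starts, and randomization comes before the first dose. Laboratory values must be no more than three weeks old, which limits how long a patient can be held back. This makes strong steering less likely. It does not remove the predictability, which costs little to avoid.

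**Conclusion.** The point holds as a weakness in concealment. An observer who tracks the assignments can know 10.5 of 44 (24%) in advance on one list, or 9.2 to 10.5 (21% to 24%) on two, and can guess the next arm correctly about 68% of the time. The two-list range rests on blocks of 6 running within each anti-PD-1 group, which is an assumption.

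A reader might also infer that the primary comparison is biased. Nothing in the documents shows this. The figures measure predictability, and any shift in the IRAE difference depends on whether staff act on it and how well they can judge IRAE risk at baseline. The point does not invalidate the design. It is an avoidable weakness that should be corrected while patients remain to be randomized.

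**What to change.** For all remaining allocations, have the statistician generate a new list with randomly varying block sizes (for example 4, 6 and 8) within the separately randomized groups of section 14.2. Remove the block size from section 5.1 and keep the sizes in a record that enrolling staff do not hold. State whether blocks run within each group, and reconcile how sections 5.1 and 14.2 define those groups. Keep what the plan already has: assignment by the statistician, one patient at a time, after checklist sign-off.

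The cost is a new list, a short amendment and a slightly larger possible imbalance. On one list the largest final difference rises from 2 patients (23:21) to 4 (24:20). On two lists it rises from 4 (24:20) to 8 (26:18), which would need both lists to stop at the worst point of a block of 8. An exact 22:22 split is not assured now either: on one list, two places into the eighth block, its probability is 3/5 = 0.60. Recomputing the Fisher power for every split from 22:22 to 26:18, in either direction, gives 78% to 82% against 79.1%, so power is practically unaffected.

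The change removes most of the certainty but not the roughly 68% guess rate. Lowering that would require accepting looser balance. If accrual is complete, report the fixed block size and its predictability as a limitation.
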